5.3 SAFETY DATA

All adverse events, reactions and serious and unexpected events/reactions will be reported immediately following the procedure noted in the protocol (section 11.2). Safety data in the form of all AEs will be presented to the DMC on a scheduled basis. This report will cover the number of events and number of subjects affected split by treatment arm and categorised by seriousness (not serious, death, is life-threatening, requires hospitalisation or prolongation of hospitalisation, persistent or significant disability or incapacity, consists of a congenital anomaly or birth deficit, important medical event or pregnancy). Frequencies of system organ class will also be presented split by treatment arm. No statistical testing of these data will be undertaken in the DMC report. These data will also be included in the final analysis report. Precipitated withdrawal symptoms will be included in the discussion section of the primary paper as a narrative in relation to the Adverse Events table. This will not be a formal analysis but to check if there is a correlation between the first 24-48 hours prior to treatment and first

month after treatment and numbers of precipitated withdrawal symptoms reported between the treatment arms.

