- the patient does not report dose-related adverse events related to the 100mg dose (e.g. sedation or lethargy, persistent headaches, nausea);
- the patient reports that 100mg is too low and they would like a dose increase, and there are no significant clinical safety concerns.

As a clinical guide, the dose should be reduced from 300 to 100mg under the following conditions:

- The patient reports XR-Bup dose-related adverse events (e.g. sedation or lethargy, persistent headaches, nausea);
- the patient is seeking to reduce their dose in an attempt to ultimately withdraw from opioid agonist treatment;
- the patient reports that 300mg is 'too high' and they would like a dose decrease, and there are no significant concerns regarding deterioration in clinical condition (e.g. substance use, physical or mental health symptoms) that may arise with a dose reduction.)

On the basis of patient report and clinical judgement of the risks and benefits, rescue dosing of Bup can be provided at any point after the first dose of XR-Bup. This will be recorded as concomitant medication.

Whilst maintenance doses will be routinely scheduled to occur every 28 days, flexibility was included in the development research for Sublocade® and this will be followed in the EXPO trial to accommodate patients who need to attend other appointments or have travel problems attending the clinic.

In summary, the protocol allows for:

- (1) the second 300mg loading dose of XR-Bup to be given after a minimum of 21 days;
- (2) each planned 100mg maintenance doses can be administered up to 2 days ahead of the scheduled dose (i.e. 26 days since the last injection); and
- (3) all subsequent doses after the first dose to be given up to 14 days after the 28-day scheduled dose (i.e. to 42 days).

Unexpected delays of up to 14 days are not anticipated to have any clinical impact on treatment response given the reported extended-release profile of the IMP.

Following the 6th dose, there is an optional consent for participants who are randomised to XR-Bup to continue receiving doses every 28 days until the date that the last participant is randomised within the EXPO Trial plus 9 months.

In summary, the dosing schedule for EXPO is shown below:

Dose	Day	Visit	Window	XR-BUP dose
1	1	Baseline	-	300mg
2	28	Week 4	21-42	300mg
3	56	Week 8	54-70	100mg or 300mg
4	84	Week 12	82-98	100mg or 300mg
5	112	Week 16	110-126	100mg or 300mg
6	140	Week 20	138-168	100mg or 300mg

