9.1.2 Optional Consents

Week 24 onwards. Participants randomised to XR-Bup can continue to receive monthly injections as detailed in section 6.3 until the date the last participant is randomised plus 9 months. The Trial Manager will inform study sites when this date is approaching. At week 24 complete all research measures as detailed in the week 24 summary. Prior to the 7th injection at week 24 the continuing XR-Bup consent form is to be completed and pregnancy test recorded as negative. Following week 24, LFT to be taken approximately every 6 months or as clinically indicated. Conmeds and Adverse Events to be recorded at each visit that XR-Bup is administered.

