6.3 INTERIM ANALYSIS

There are no planned interim analyses and as such the study is not powered to achieve these. There are no planned stopping criteria based on efficacy and stopping based on safety will be guided by the DMC.

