APPENDIX 2 – OBJECTIVES AND ASSOCIATED OUTCOME MEASURES AND CHARACTERISTICS

Objective	Outcome Measure	Time Period	End point	Variable Type	Analysis Model	Scoring
One - effectiveness of BUP-XR and MET/BUP-SL	Primary outcome					
	Number of days abstinent from heroin	Days 8 – 168	24 weeks	Count	Poisson Regression	Count of days abstinent
	Secondary outcomes					
	Number of days abstinent from cocaine	Days 8 – 168	24 weeks	Count	Poisson Regression	Count of days abstinent
	Number of days abstinent from Benzodiazepines	Days 8 – 168	24 weeks	Count	Poisson Regression	Count of days abstinent
	Longest time in days continuously abstinent from heroin	Days 8 – 168	24 weeks	Count	Poisson Regression	Max Count of days consecutively abstinent
	Longest time in days continuously abstinent from cocaine	Days 8 – 168	24 weeks	Count	Poisson Regression	Max Count of days consecutively abstinent
	Longest time in days continuously abstinent from Benzodiazepines	Days 8 – 168	24 weeks	Count	Poisson Regression	Max Count of days consecutively abstinent
Two – Safety profile	Number of safety events	Study enrolment to 24 weeks	24 weeks	Count	Descriptive	n/a
Three – Treatment retention	Total retention time	Days 8 – 168	24 weeks	Count	Poisson Regression	Count of Days enrolled in maintenance medication for OUD
	Survival time to study withdrawal	Randomisation date to first discontinuation	24 weeks	Time to event	Cox regression	Time to first discontinuation
Four – OUD and CUD remission status	SCID-RV interview	Baseline to week 24	12 weeks & 24 weeks	binary	(Binary) logistic regression	Remission status (Yes/No) indicated by SCID-RV (see appendix 3 for SCID scoring)

Objective	Outcome Measure	Time Period	End point	Variable Type	Analysis Model	Scoring
Five – Clinician rated impression of patient response to treatment	Clinical Global Impression scale (severity and improvement - CQI-S/CGI-I)	Baseline to week 24	24 weeks	Ordinal	Ordinal logistic Regression	See Appendix 3
	Addiction Dimensions for Assessment and Personalised Treatment (ADAPT)	Baseline to week 24	24 weeks	Continuous	GLM	See Appendix 3
Six – Patient reported recovery outcomes	Craving response using Craving experience questionnaire (CEQ-F)	Baseline to week 24	24 weeks	Continuous	GLM	See Appendix 3
	Visual analogue craving rating (Need) (VAS-N)	Baseline to week 24	24 weeks	Continuous	GLM	See Appendix 3
	Visual analogue craving rating (Want) (VAS-W)	Baseline to week 24	24 weeks	Continuous	GLM	See Appendix 3

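### SAP 5.3 sets no time window for by-arm adverse event tables, although scheduled recording after week 24 continues only for XR-Bup participants

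*SAP*

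**What the plan says.** **Who is followed after week 24.** Protocol 9.1.2 opens the extension to one randomised treatment only: "Participants randomised to XR-Bup can continue to receive monthly injections". Protocol 6.3 sets its end: "until the date that the last participant is randomised within the EXPO Trial plus 9 months". The synopsis gives a maximum treatment duration of 40 months. For this period Protocol 9.1.2 says: "Conmeds and Adverse Events to be recorded at each visit that XR-Bup is administered". The assessment schedule (Protocol 9.2, repeated in SAP 5.1) gives oral-arm participants no study visit after week 24.

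**What is tabulated.** On the DMC report, SAP 5.3 says "Safety data in the form of all AEs will be presented to the DMC on a scheduled basis" and "This report will cover the number of events and number of subjects affected split by treatment arm". It mentions no period, rate or exposure. It rules out statistical testing in the DMC report and says that the same data also go into the final analysis report. SAP 5.2, Objective 2, lists a tabulation by group, again without a period. SAP Appendix 2 does give a period for the number of safety events: "Study enrolment to 24 weeks", with a 24-week end point and descriptive analysis.

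**What the tables are for.** Safety of XR-Bup is among the secondary objectives on which the groups are compared (SAP 3.2). There is no efficacy stopping rule, and "stopping based on safety will be guided by the DMC" (SAP 6.3).

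**The concern.** A table of raw event counts by arm is a fair comparison only if the arms are observed for about the same time. Randomisation is 1:1, so this holds up to week 24. Beyond that point the XR-Bup column can keep growing while the oral column has no scheduled source of new events. With identical true event rates, the table would still show more events under XR-Bup, and the gap would widen as more participants enter the extension.

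The DMC is the body most exposed to this, because it guides safety stopping and no part of the SAP limits its tables to a common period. For the final report, a programmer working from SAP 5.3 and one working from Appendix 2 could produce different tables for the same secondary objective.

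**Working it through.** The plan states no figure on this point, so there is none to reproduce. The check compares the passages and then estimates the scale.

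**1. Observation time.** Up to day 168 both arms have scheduled recording. After day 168 only XR-Bup continuers do. Protocol 11.2 also has the log reviewed after occurrences between visits, so an oral-arm event after week 24 could still be entered. There is no scheduled contact that would find it.

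**2. Window by table.**

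| Table | Governing text | Window |
|---|---|---|
| DMC report | SAP 5.3 | none stated |
| Final report | SAP 5.3, same data carried forward | none stated |
| Final report | SAP Appendix 2 | enrolment to 24 weeks |

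SAP 5.2 sends extension-phase retention to a separate SAP. No matching statement is made for safety.

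**3. Scale: inputs.**
- Recruitment starts July 2019 (Protocol 5.2), month 0. It pauses March to July 2020 (SAP 6.9), months 8 to 12. The last patient is recruited about October 2021 (SAP 6.1), month 27.
- The extension ends 9 months later, at month 36, close to the planned database lock of June/July 2022.
- Week 24 is 168/30.4375 = 5.52 months.
- Assumed: uniform entry outside the pause; constant event rate; no dropout before week 24; a share *c* of XR-Bup participants continues, for a fraction *s* of the time available to them.

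**4. End of extension (month 36).**
- Mean entry = (8 × 4 + 15 × 19.5)/23 = 14.11 months.
- Mean available time after week 24 = 36 − 14.11 − 5.52 = 16.37 months (range 9 − 5.52 = 3.5 to 36 − 5.52 = 30.5).
- Share of XR-Bup events outside the oral window = 16.37*cs*/(16.37*cs* + 5.52).
- Ratio of XR-Bup to oral event counts with equal true rates = 1 + 16.37*cs*/5.52.

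**5. DMC cut at month 18.** The documents give no DMC dates, so this cut is illustrative. Entry covers months 0-8 and 12-18, 14 months in all.
- Mean time after week 24 = (8 × 8.48 + 0.48²/2)/14 = 4.85 months.
- Mean time within the window = (8 × 5.52 + 0.48 × 5.52 + 5.52²/2)/14 = 4.43 months.
- The formulas are as in step 4, with 4.85 and 4.43 in place of 16.37 and 5.52.

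| *c* | *s* | Share, month 18 | Ratio | Share, month 36 | Ratio |
|---|---|---|---|---|---|
| 10% | 0.5 | 5% | 1.05 | 12.9% | 1.15 |
| 20% | 0.5 | 10% | 1.11 | 22.9% | 1.30 |
| 30% | 1 | 25% | 1.33 | 47.1% | 1.89 |
| 50% | 1 | 35% | 1.55 | 59.7% | 2.48 |

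Below this grid, 10% continuing for a quarter of the available time gives 0.41/(0.41 + 5.52) = 6.9% at month 36.

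**6. A hint on uptake.** Protocol 9.1.2 plans extension interviews with about 60 XR-Bup participants from two sites, 12-24 months after randomisation. Against 152 + 150 = 302 planned XR-Bup participants, that is 20%. If they stayed only to month 12, the extra time would average 0.20 × (12 − 5.52) = 1.3 months, or about 19% of all XR-Bup observation time.

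**7. With the Appendix 2 window.** Scheduled observation is 168 days in each arm before dropout, a ratio of 1.0.

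**The case against.** The strongest reply is that the final report already has its window. SAP 5.2 points to Appendix 2 for further detail on each outcome measure, and Appendix 2 gives 24 weeks. Read together, the appendix supplies what 5.3 leaves out. This largely stands. A reader might infer that the final XR-Bup counts will include months that the oral arm lacks; the documents do not establish that. What remains is that 5.3 carries an unlimited data set into the same report without citing the appendix.

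Second, the reference to all AEs may mean all types of event, serious or not, instead of all calendar time. That reading is reasonable, but it leaves the DMC tables with no stated period.

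Third, the DMC works under a charter (Protocol section 14) that is not among the documents and may set data cuts. The extension is openly described, no testing is done on DMC data, and no numerical safety boundary could be crossed by unequal counts. All of this lowers the risk of a wrong decision. It does not put the arms on equal time in a table that the SAP itself specifies.

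Fourth, the large figures belong to the end of the extension, whereas the reports that lack any window are mostly earlier. This is right, and it is why the month-18 column is shown. A reader might infer from the month-36 column that the distortion always exceeds 10%. It does not: the lowest case is about 5% at month 18, and lower uptake takes even the month-36 figure below 10%. Events that cluster early, such as the precipitated withdrawal that SAP 5.3 itself examines around the start of treatment, would lower the shares further. Subjects affected rise less than event counts, because a participant is counted once.

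**Conclusion.** The point holds for the DMC tables: as specified, they can combine unequal scheduled observation with raw counts by arm, and nothing in the SAP corrects for it. For the final report it is an internal inconsistency between SAP 5.3 and Appendix 2, and an excess would arise only if 5.3 were followed as written.

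Over the scenarios shown, about 5-35% of XR-Bup events would lie outside the oral window at month 18 and about 13-60% at the end of the extension. These ranges rest on assumed uptake, length of stay, uniform entry and a constant event rate, and they concern event counts only. The direction is clear: any uptake adds recording time to one arm. The size is not known from the documents. Safety is analysed descriptively, so the consequence is a misleading table, not a false test result.

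**What to change.** State in SAP 5.3 that every by-arm safety table, for the DMC and for the final report, covers the Appendix 2 period (enrolment to week 24, day 168) in both arms. Extension-phase XR-Bup events then go in a separate single-arm table with person-time and no comparison column, so the DMC still sees every event.

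The cost is one sentence in the SAP and a date filter in the table program. Data collection, safety reporting duties and participant management do not change.

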6.5 IMP risks

The Reference Safety Information (RSI) for all information pertaining to IMP risk for the XR-Bup will be set out in the manufacturer's Investigators Brochure (IB). The SmPC will be the reference document for Bup/Met.

Adverse reactions (commonly associated in 5% or more of patients) receiving XR-Bup are: (a) constipation; (b) nausea; (c) vomiting; (d) headache; (e) fatigue; (f) increased hepatic enzymes; (g) injection site pain; (h) injection site pruritis.

Drug-drug interactions potentially relevant to the IMP (with Bup and XR-Bup) are as follows:

Drug Class	Drug(s) within Class	Clinical effect and suggested management
Benzodiazepines and Other Central Nervous System (CNS) Depressants	Alcohol, non-benzodiazepine sedatives/hypnotics, anxiolytics, tranquilizers, muscle relaxants, general anaesthetics, antipsychotics, and other opioids	
 - Increases the risk of respiratory depression, profound sedation, coma, and death. - Use of these substances should be stabilised during treatment with Bup products. Patients should be advised of the danger of concomitant use of sedatives while participating in the trial.
CYP3A4 inhibitors:	Macrolide antibiotics (e.g. erythromycin) Azole-antifungal agents (e.g. ketoconazole) Protease inhibitors (e.g. ritonavir)	
 - Effects of CYP3A4 inhibitors on Bup exposure in participants treated with XR-Bup have not been studied with Bup, however, such interactions have been established. - In the presence of CYP3A4 inhibitors, monitor for signs and symptoms of Bup toxicity or overdose. - Monitor for Bup withdrawal if the concomitant medication is discontinued after the patient is stable on. - The dose of either Bup or the CYP3A4 inhibitor may need to be adjusted accordingly.
CYP3A4 Inducers	Rifampin Carbamazepine Phenytoin	
 - Effects of CYP3A4 inducers on Bup exposure in participants treated with XR-Bup have not been studied, however, CYP3A4 inducers may induce its metabolism and lead to decrease in Bup plasma concentrations. - Monitor for signs and symptoms of Bup toxicity or overdose, if the CYP3A4 inducers is discontinued after the patient is stable on XR-Bup. The dose of either Bup or the CYP3A4 inducer may need to be adjusted accordingly.

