9.2 Assessments by Study Week and Study Timeline

Measure	Baseline	Randomisation	Ongoing	Week 1	Week 2~	Week 4	Week 6~	Week 8	Week 10~	Week 12	Week 14~	Week 16	Week 18~	Week 20	Week 22~	Week 24	Withdrawal	Week 24 onwards	Ext. Phase Interview ++
Consent §	X																	X	X
Screening	X																		
UDS				X	X	X	X	X	X	X	X	X	X	X	X	X			
LFT *	X					X			X						X			X	
XR-Bup**			X	X		X	X		X	X		X	X					X	
Bup/Met **		X																	
ALC-QFM (TOP)***	X															X			
SCID-5-RV	X								X						X				X
ADAPT	X				X				X						X				
CGI-S	X																		
CGI-I						X			X						X				
CEQ-F – H***	X					X		X	X	X		X	X	X	X				
CEQ-F – C***	X					X		X	X	X	X		X	X	X				
VAS-N (H/C)***	X					X		X	X	X	X		X	X	X				
VAS-W (H/C)***	X					X		X	X	X	X		X	X	X				
DERS-SF	X					X			X						X				X
WSAS	X					X			X						X				
EQ-5D-5L	X								X						X				
AD-SUS	X									X					X				
KCF***						X			X						X				
QIDS-SR	X					X			X						X				
SURE								X		X					X				
PRO-S	X																		
PRO-I								X		X					X				
MoCA***	X									X									
OSTQOL																		X	
PHQ-4																		X	
PHQ-15																		X	
Exit Interview+																X			
Bup/Met + PSI Interview++															X				
TLFB	X	X																	X
Con Meds****		X				X				X					X			X	
Adverse Events Log		X																X	
Research Payments	X		X	X	X	X	X	X	X	X	X	X	X	X	X	X		X	
*****	20		10	10	10	5	10	10	10	5	10	10	5	10	10	10	5	10	20

§ screening to include pregnancy test, demographics and medical history. Participants receiving XR-Bup reconsented once at week 24 to continue receiving monthly injections;

* LFT for all participants at screening; during treatment for XR-Bup participants only under protocol;

** refer to section 6 of the protocol for guidelines;

*** used for mediation model;

**** ConMeds to be recorded continuously and reviewed at week 4, 12 and 24;

***** research payments are time offset to attend the clinic to complete research measures and cover travel (either a £20, £10, or £5 value, as detailed per visit applicable; loaded onto a prepaid card).

- + Exit Interview conducted at South London, Newcastle, West Midlands and Tayside sites with XR-Bup participants only. Participants will be reimbursed an additional £20 for their time in taking part in the interview (loaded onto a prepaid card).

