9.3 Laboratory Tests

Each site will determine all participants' liver function (as defined in the inclusion/exclusion criteria) after consent either by conducting an LFT (serum) blood-test following their local laboratory procedure, or accessing this information from the participant's hospital medical records if a prior LFT test result has been done and recorded within 12 weeks from the date of screening. During post-randomisation 6-month treatment phase, participants allocated to the XR-Bup arm will be asked to have further LFT testing at visits 4, 12 and 24, or more often as judged by the CI or PI. After the post-randomisation 6-month treatment phase, participants who consent to continue having XR-Bup injections will be asked to have further LFT testing approximately every 6 months or more often as judged by the CI or PI.

If the participant does not have their bloods taken post randomisation for any reason (i.e., including but not limited to, participant refusal, they do not attend the visit or if it is not possible to take bloods); they may continue in the trial at the discretion of the PI or Sub Investigator based on their clinical judgement. Participants randomised to BUP or Met in the study will have LFT testing according to their local standard of care.

10. Assessment of Efficacy

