11.1 Specification, timing and recording of safety parameters

For participants assigned to XR-Bup, LFT (blood sampling) will be done at screening (or recorded from the participants medical records if an LFT procedure was done no more than 12 weeks before consent), and at 4-weeks, 12-weeks and end of study (24-weeks). Participants who consent to receive XR-Bup treatment past 6 injections, a LFT will be taken every 6 months.

If a participant does not have their bloods taken for any reason post randomisation (i.e., including but not limited to, participant refusal, they do not attend the visit or if it is not possible to take bloods); they may continue in the trial at the discretion of the PI or Sub Investigator based on their clinical judgement. The CI or PI may judge that more frequent LFT monitoring is clinically indicated for these and other participants in the study.

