5.1 TIME POINTS OF OUTCOMES MEASURES

Table 2 indicates the data and study measures to be collected during the trial and at which time points across the study they are collected.

Table 1: List of outcome measures to be collected and time point of collection

Measure	Baseline	Randomisation	Ongoing	Week 1	Week 2	Week 4	Week 6	Week 8	Week 10	Week 12	Week 14	Week 16	Week 18	Week 20	Week 22	Week 24	Withdrawal	Week 24 onwards	Ext. Phase Interview ++
Consent §	X																	X	X
Screening	X																		
UDS				X	X	X	X	X	X	X	X	X	X	X	X				
LFT *	X					X				X						X		X	
BUP-XR**				X		X		X		X		X		X				X	
BUP-SL/MET **		X																	
ALC-QFM (TOP)***	X																X		
SCID-5-RV	X									X						X			X
ADAPT	X					X				X						X			
CGI-S	X																		
CGI-I						X				X						X			
CEQ-F – H***	X					X		X		X		X		X		X	X		
CEQ-F – C***	X					X		X		X		X		X		X	X		
VAS-N (H/C)***	X					X		X		X		X		X		X	X		
VAS-W (H/C)***	X					X		X		X		X		X		X	X		
DERS-SF	X					X				X						X			X
WSAS	X					X				X						X			
EQ-5D-5L	X									X						X			
AD-SUS	X									X						X			
KCF***							X			X						X			
QIDS-SR	X					X				X						X			
SURE							X			X						X			
PRO-S	X																		
PRO-I								X			X					X			
MoCA***	X									X									
OSTQOL																		X	
PHQ-4																		X	
PHQ-15																		X	
Exit Interview+																	X		
BUP-SL/MET + PSI Interview++																X			
TLFB	X	X																	X
Con Meds****		X				X				X						X		X	
Adverse Events Log		X																X	
Research Payments *****	X		X	X	X	X	X	X	X	X	X	X	X	X	X			X	
	20		10	10	10	5	10	1	10	5	10	10	10	5	10			20	

§ screening to include pregnancy test, demographics and medical history. Participants receiving XR- BUP-SL reconsented once at week 24 to continue receiving monthly injections;

* LFT for all participants at screening; during treatment for BUP-XR participants only under protocol;

** refer to section 6 of the protocol for guidelines;

*** used for mediation model;

**** ConMeds to be recorded continuously and reviewed at week 4, 12 and 24;

***** research payments are time offset to attend the clinic to complete research measures and cover travel (either a £20, £10, or £5 value, as detailed per visit applicable; loaded onto a prepaid card).

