	Day 1	day 2	Day 3	Day 4		Day 13	Day 14	Day 15	Day 16	Day 17
Self-report	drug use	drug use	drug use	drug use		no drug use	no drug use	no drug use	no drug use	drug use
UDS (Day 4 and day 16)				positive						negative

Figure 6: Example 3 of Self-report and UDS results

Outcome:	Day 1	day 2	Day 3	Day 4		Day 13	Day 14	Day 15	Day 16	Day 17
	drug use	drug use	drug use	drug use		no drug use	no drug use	no drug use	no drug use	drug use

Figure 7: Self-report and UDS example 3 outcome

The syntax for calculating this variable will be validated and verified fully prior to database lock.

During a data review it was identified that some participants had been called in for their last visit early, resulting in the full primary outcome of 161 days not being obtained. The participants in question are not lost to follow up or withdrawals and are just missing due to an administration error and in most cases only by a day or two. It was noted that patient records could provide data for some of these missing days therefore, with input from independent committees, it was decided that for the TLFB data some of the final follow up days are being input based on these medical notes.

Where the TLFB data is not obtainable from the patient notes, the missing days will be imputed using a devised rule. The missing data rule used for these missing days will look at the last 14 days of data that are available for the participant, the percentage of drug use will be calculated. For all missing days a random number will be generated (either a 0 or 1, no use or use) using a probability based on their percentage used in the last 14 days.

Measure 2; Longest time in days *continuously* abstinent from 'substance' during days 8-168 (weeks 2 to 24, 161 days); combining self-report information from time-line follow-back and 12 urine drug screen (UDS) results.

- Longest count of days continuously abstinent from illicit/non-medical opioids
- Longest count of days continuously abstinent from cocaine
- Longest count of days continuously abstinent from benzodiazepines

Secondary objectives;

Objective 1 – Clinical superiority of BUP-XR plus PSI versus BUP-SL/MET plus PSI.

Will be analysed as part of phase 2 of the study and detailed in a separate SAP

Objective 2 - Safety profile

- Tabulation of AEs, ARs, SAEs, SARs and SUSARs in each group

Objective 3 - Treatment retention

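### On-treatment liver tests are scheduled for XR-Bup participants only, so the by-arm adverse-event tables can show an XR-Bup excess produced by testing alone

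*SAP*

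**What the plan says.** **Testing schedule.** Everyone has an LFT result at screening. After randomisation, Protocol 9.3 states that "participants allocated to the XR-Bup arm will be asked to have further LFT testing at visits 4, 12 and 24", or more often if the investigator judges it necessary. For the oral arms it states: "Participants randomised to BUP or Met in the study will have LFT testing according to their local standard of care". The footnote to the schedule in Protocol 9.2 says the same ("LFT for all participants at screening; during treatment for XR-Bup participants only under protocol"), and the SAP repeats it under its own schedule in 5.1 ("LFT for all participants at screening; during treatment for BUP-XR participants only under protocol"). Beyond week 24, Protocol 11.1 adds: "Participants who consent to receive XR-Bup treatment past 6 injections, a LFT will be taken every 6 months".

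**Expected reaction.** Protocol 6.5 gives a list introduced by "Adverse reactions (commonly associated in 5% or more of patients) receiving XR-Bup are". Raised hepatic enzymes are on it.

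**Safety outputs.** SAP 3.2 places the safety of BUP-XR (the SAP's name for XR-Bup) among the secondary objectives on group differences. SAP 5.2 defines the output as "Tabulation of AEs, ARs, SAEs, SARs and SUSARs in each group". SAP 5.3 gives events and participants affected by arm and by seriousness category, and adds: "Frequencies of system organ class will also be presented split by treatment arm". These tables go to the DMC without testing and appear again in the final report. SAP Appendix 2 classes the safety analysis as descriptive, from enrolment to 24 weeks.

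**What is not there.** Neither document says when an abnormal LFT becomes an adverse event, separates events found by LFT, reports how many participants were tested in each arm, or plans any analysis of the LFT values.

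**The concern.** A rise in liver enzymes that causes no symptoms is recorded only if someone takes blood. One arm has three scheduled chances to find it within the 24-week safety window. The other has however many local practice provides. A by-arm table that ignores this mixes two quantities: how often the event happens and how hard it was looked for. The affected event is one the protocol already expects with XR-Bup, so readers will look for it.

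The risk runs both ways. An excess created by testing could be read as XR-Bup hepatotoxicity, and a real hepatic signal could be dismissed as surveillance. The planned outputs would not let the DMC or a reader tell these apart.

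The SUSAR row has a separate comparability problem. Whether a serious reaction counts as unexpected depends on the reference document, and the two arms are judged on different terms.

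**Working it through.** The documents give no figure to reproduce, so the check is an illustration of the mechanism followed by a comparison of the SUSAR definitions.

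**Inputs**

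| Input | Value | Source |
|---|---|---|
| Participants per arm, n | 152 | Protocol 5.2 (groups 1 and 2) |
| True risk of an LFT-only event, p, the same in both arms | 5% or 10% | Assumed; the 5% in Protocol 6.5 is a floor for XR-Bup only |
| Share detected on XR-Bup, dX | 100%, or 85% to allow for missed bloods | Assumed; Protocol 9.3 and 11.1 allow continuation without bloods |
| Share detected in the oral arm, dO | 0%, 25%, 50% or 100% | Assumed; no local testing rate is given |

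It is also assumed that each detected case is logged as an adverse event.

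**Formulae**

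- Expected recorded cases: n × p × dX on XR-Bup and n × p × dO in the oral arm.
- Spurious gap in percentage points: 100 × p × (dX − dO).

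For example, with p = 5%, dX = 100% and dO = 25%, XR-Bup has 152 × 0.05 × 1 = 7.6 recorded cases and the oral arm has 152 × 0.05 × 0.25 = 1.9. The gap is 100 × 0.05 × 0.75 = 3.75 points.

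**Full detection on XR-Bup**

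| True risk | Recorded, XR-Bup | Recorded, oral arm, at 0 / 25 / 50 / 100% | Gap (points) |
|---|---|---|---|
| 5% | 7.6 | 0 / 1.9 / 3.8 / 7.6 | 5.0 / 3.75 / 2.5 / 0 |
| 10% | 15.2 | 0 / 3.8 / 7.6 / 15.2 | 10.0 / 7.5 / 5.0 / 0 |

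**85% detection on XR-Bup**

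| True risk | Recorded, XR-Bup | Gap (points) at 0 / 25 / 50 / 100% oral-arm detection |
|---|---|---|
| 5% | 6.5 | 4.25 / 3.0 / 1.75 / −0.75 |
| 10% | 12.9 | 8.5 / 6.0 / 3.5 / −1.5 |

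True risk is equal throughout, so every non-zero gap comes from detection. The gap vanishes when dX = dO and reverses when dO is the larger.

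**SUSARs.** Protocol 6.5 makes the Investigator's Brochure the safety reference for XR-Bup and the SmPC the reference for Bup and Met. Protocol 11.2 then treats every serious adverse reaction (SAR) in the XR-Bup groups as unexpected. On XR-Bup, therefore, the SUSAR count equals the SAR count by construction. In the oral arm a SAR consistent with the SmPC is not a SUSAR, so the SUSAR count can be lower than the SAR count. A difference between arms in the SUSAR row partly reflects the reference rule.

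**The case against.** The strongest reply is that the excess rests on two conditions the documents do not settle: that abnormal LFTs are entered as adverse events, and that local care tests oral-arm patients less often. Protocol 11.2 gives only the general definition of an adverse event, and Protocol 9.3 gives no local testing rate. That stands. A reader might infer that an XR-Bup excess is bound to appear, or that oral-arm patients go untested. The documents support neither: the excess is possible, and its size is unknown.

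Second, the tables are descriptive. A reader might be tempted to attach p-values to a hypothetical split of cases against none and speak of false-positive findings. SAP 5.3 rules out testing in the DMC report and Appendix 2 plans description only, so such p-values match no planned analysis. That also stands. A descriptive table still informs the DMC and readers of the final report, however.

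Third, SAP 5.3 splits events by seriousness. A silent enzyme rise would normally fall in the non-serious category, so the documents do not support a claim that LFT testing distorts the serious-event comparison.

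Fourth, any bias of this kind would usually count against the experimental drug, and the unequal schedule is openly stated in both documents. This limits the harm. It does not help a reader judge whether an observed excess is real, because no planned output shows who was tested.

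On SUSARs, a reader might infer that identical serious reactions always count in one arm only. That is too strong. An oral-arm SAR inconsistent with the SmPC is also a SUSAR, and the imbalance concerns SARs that the SmPC lists.

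**Conclusion.** The point holds as a weakness in the planned safety tables. Liver testing after randomisation is unequal by design, adverse events are displayed by arm, and nothing in the SAP allows for the difference. Under the stated assumptions, testing alone could produce a gap of 2.5 to 5.0 points at 5% true risk, or 5.0 to 10.0 points at 10%, when local care detects between half and none of the cases. The gap is zero with equal detection. Missed XR-Bup bloods narrow it and can reverse it slightly. These figures are illustrations, because the documents give neither the true risk nor the local detection rate.

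The consequence is a table that can mislead, mainly for non-serious hepatic and laboratory events. The by-arm SUSAR count is not comparable whatever the LFT testing rate. Neither issue touches the primary outcome.

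**What to change.** In SAP 5.3:

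1. Flag adverse events found only through an LFT, in both arms, whether the test was protocol-scheduled or local. Show the by-arm adverse-event, adverse-reaction and system-organ-class totals with and without them. Do not simply remove events found by the scheduled tests. That would delete genuine XR-Bup reactions while oral-arm events found by local tests stayed in, which is the opposite bias.
2. Give the number of participants in each arm with at least one on-treatment LFT, where available. Add a footnote on the unequal testing and on how abnormal results came to be logged as adverse events.
3. Summarise ALT, AST and bilirubin at weeks 4, 12 and 24 against baseline within XR-Bup. Include counts above the limits in Protocol 8.2: ALT or AST more than three times the upper limit of normal, and bilirubin above the local normal range. Note that the screening result may be up to 12 weeks old (Protocol 9.3).
4. Present SUSARs as a regulatory listing. Rest the between-arm serious-event comparison on the SAEs and SARs that SAP 5.2 already tabulates.

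The cost is SAP wording, one extra table and some review of adverse-event records. Protocol 11.2 describes assessments of seriousness, causality and intensity but no field for how an event was detected, so that would have to be established from the records. No new blood tests and no change to care are needed.
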